5.3 STEP-YA Intervention

STEP-YA is delivered in a single 90-minute synchronous videoconference session using HIPAA compliant Zoom technology⁴⁶⁻⁴⁸ licensed to our cancer center. Interventionists with graduate level training in psychology, social work, or closely aligned discipline (e.g., human development,

nursing) will be trained and supervised by psychologists with CBTI expertise to deliver the STEP-YA intervention following a structured outline. The interventionist will deliver STEP-YA in a 1 on 1 session using a slide deck of 47 slides and following a structured outline. During the session, the participant is able to see and hear the presenter, view the presentation slides, and ask questions. To support participants in developing and implementing their sleep action plan, take-home materials including a copy of the presentation slides and sleep action plan template are provided by email. The presentation begins with educational information on the problem of insomnia after cancer and the 3-P model before presenting specific suggestions for improving sleep in YACS. These suggestions are based on CBTI components of sleep hygiene, stimulus control, and cognitive restructuring.^{27, 32, 49-51} To aid comprehension, this material is presented in four sections addressing 1. Lifestyle issues, (e.g., benefits of exercise and limiting alcohol), 2. Sleep environment (e.g., importance of a dark, quiet bedroom; avoiding bed for non-sleep activities), 3. Sleep timing (e.g., regular wake time, avoiding napping) and 4. Managing expectations and challenges (e.g., sleep worry, physical symptoms, social pressures). For each suggestion, an underlying rationale and potential benefit are presented. Both the look and content of the STEP-YA material are targeted to appeal to YACS. For example, text describing the benefits of exercise are accompanied by photos of young adults engaged in traditional and contemporary exercises, (e.g., yoga, spin class, cross-fit), and the description of the effects of caffeine includes photos of products YACS commonly consume (e.g., energy drinks, green tea, sodas, coffee drinks). In section 4, examples of the social, developmental and health challenges that YACS may encounter are noted, along with suggestions for managing them. These include living spaces shared with roommates or parents, social pressures, “fear of missing out,” and tendency toward a delayed sleep phase common in young adults, as well as physical health symptoms such as pain, or hot flashes. At the conclusion of each section (e.g., lifestyle), the participant is asked to review the suggestions in the section and complete their sleep action plan template to record their current sleep practices and behavioral changes they intend to make. Action plans of this kind are central to self-management education³⁵ and have been shown to increase successful behavior change.^{52, 53} To close the session, the presenter offers examples of STEP-YA suggestions implemented in a daily routine, and asks the participant to review and revise their sleep action plan, including anticipating challenges and planning strategies to manage them.

5.4 Behavioral Coaching

Participants randomized to the coaching condition will receive 2 individualized remote coaching sessions 1, and again 2 weeks following their STEP-YA session. Optimal timing for coaching sessions is 7 and 14 days after the STEP-YA session, but may be scheduled between 5-23 days after the STEP-YA session with at least 5 days between coaching sessions. Paraprofessional coaches trained and supervised by psychologists with CBTI expertise will follow a structured outline adapted from a previous self-management intervention at our center.⁵⁴ In the sessions, designed to last approximately 30 minutes, coaches ask participants to review their progress and challenges implementing their sleep action plan. Coaches offer support and encouragement and may refer participants to the take-home materials to help answer questions and reinforce program goals and suggestions. Following, principles of self-care management and previous coaching interventions successful with cancer survivors,^{44, 55-58} coaching sessions are not prescriptive, but support YACS to use self-management skills including decision-making, goal-setting, self-assessment, and problem solving to help them implement their individual sleep action plan. Administrative data on coaching session duration, and sessions missed, interrupted, or rescheduled will be collected.

5.5 Study Measures

All measures were previously used with cancer survivors on DFCI 15-336. Measures can be found in Appendix B. Measures are given at all timepoints unless otherwise noted.

The Insomnia Severity Index (ISI)⁵⁹: The 7-item ISI is the most commonly used measure in insomnia research and has been validated in cancer populations.⁶⁰ It has demonstrated adequate internal consistency, and is sensitive to detect changes in perceived sleep difficulties with treatment.

Profile of Mood States – Short Form (POMS-SF)⁶¹: The Profile of Mood States-Short Form is a commonly used measure of psychological distress that has been validated in cancer populations.⁶² It is a 35-item measure which assesses the mood states of participants, and provides multiple scales including an overall Total Mood Disturbance (TMD) score used here.

Physical Health: Physical health will be assessed with one item from the commonly-used SF-12⁶³ asking respondents to rate their overall health. Pain will be measured with the commonly used Pain Thermometer⁶⁴ on which participants rate their pain on a scale of 1-10, and a single item asking participants to rate whether they feel “in pain” on a five-point scale.

Sleep Treatment Change: Participants will be asked to report any changes made in sleep behaviors during the study period including those not specifically recommended by the study interventions (e.g., new sleep medications, new non-study meditation class). This measure is only completed at post-intervention timepoints.

Demographics and Medical History: Demographic information, medical information (e.g., cancer diagnosis and treatment, recent psychiatric treatment), and insomnia history (e.g., insomnia duration, burden, past treatments) will be collected by direct patient report. The 5-item Morningness-Eveningness Questionnaire (Reduced)⁶⁵ will also be included to identify participants’ circadian tendencies. This measure is only given at baseline.

Intervention Evaluations: Participants will complete evaluations at several timepoints. 1) At the end of the intervention session, participants will report on ease of use and acceptability using checklist items adapted from the Telehealth Usability Questionnaire⁶⁶ and satisfaction will be assessed with checklist items adapted from [name] previous survivorship education trials. 2) Participants who are randomized to the coaching condition will complete a brief satisfaction evaluation of the coaching sessions after the second coaching phone call. 3) All participants will complete a brief questionnaire to provide their feedback about the intervention and how it could be improved at the 8-week post-intervention timepoint.

Steps to insure complete data: Participants will complete baseline measures online using Qualtrics at the intervention session prior to randomization to insure completeness. Following procedures found to be effective in [name] DFCI protocols 17-515, 15-336 and 14-583, the study also makes use of scheduled telephone appointments to insure timely completion of the follow-up assessments. In previous intervention studies, telephone appointments have been highly effective for encouraging survivors to complete assessments; we have achieved 100% complete data for primary endpoints and 95% complete data overall using this method.

5.6 OnCore Registration

As per DF/HCC SOP REGIST-101A, with the approval of the Director of the Office of Data Quality, retrospective registration will be utilized for this minimal risk study.

Institutions will register eligible participants in the Clinical Trials Management System (CTMS) OnCore as required by DF/HCC SOP REGIST-101. When required by REGIST-101, registration must occur prior to the initiation of protocol-specific procedures or assessments.

Registration requires a signed informed consent document and a completed eligibility checklist according to DF/HCC SOP REGIST-104.

6.0 RISKS AND ADVERSE REACTIONS AND THEIR MANAGEMENT

Potential for some participants to experience increased daytime fatigue from the study intervention

The primary risk of this minimal risk study for participants is a brief (1-2 week) period of daytime fatigue, which is the result of sleep scheduling (i.e., reducing daytime sleep).

Consequently, participants may experience some physical and mental side effects associated with sleepiness. However, these side effects should be similar to the effects of sleepiness they have previously experienced due to their insomnia. In order to address and mitigate this risk, the STEP-YA intervention provides information about anticipating and planning management strategies to cope with increased symptoms of fatigue that may occur. In particular, instructions will be provided to maintain personal safety by avoiding driving at times when participants are likely to become sleepy, and taking appropriate steps if they become sleepy while driving. Specifically, participants are instructed that they should immediately pull over to a safe area, stop driving and sleep if they become fatigued while driving. Additionally, participants will be provided with the contact information of the PI, [name], a licensed psychologist with extensive clinical experience with cancer survivors and insomnia treatment. Participants who have any concerns about the study are encouraged to contact him for assistance.

Privacy and Confidentiality

We have taken steps to protect the privacy of participants during all aspects of intervention delivery and data collection.

The Zoom videoconferencing technology which will be used to conduct eligibility screening conversations and deliver the online intervention is fully HIPAA compliant. The platform is licensed to our cancer center, and is currently used for telehealth visits, research visits, educational webinars, and study meetings. As of June 2020, Zoom is encrypted using AES 256-bit GCM encryption standard, the strongest and most robust encryption standard that is currently commercially available. For additional security, our institution has locked the password function so that passwords are required for all Zoom meetings. A new individual password is created for each session, which is then embedded into the link sent to the participant. This enables the participant to access the session securely without having to enter a password, while ensuring that only the participant has access to the meeting. Once the participant enters the meeting, the meeting will be locked which provides further protection against any other person entering the meeting either accidentally or intentionally.

The Qualtrics web-based survey platform that will be used to collect study data remotely has been used successfully by [name] for other online intervention studies, including a recently completed study for young adult cancer survivors (DFCI protocol 17-515). The Qualtrics platform is available through the Harvard Medical School which provides access to a licensed version to all HMS faculty and staff as well as affiliated institutions. Qualtrics is the leading global provider of data collection and analysis for academic research, serving over 5,000 customers in 75 countries. The Qualtrics platform can deliver web and mobile surveys, embed videos in a larger survey, send email and mobile reminders, and automate the data collection procedures. Qualtrics provides secure collection of survey data using encrypted data transfer and complies with HIPAA protections for privacy of patient information. In our application for this study, the Qualtrics program will identify participants only by study ID, and will contain no identifiers. Participants will access the Qualtrics platform through a unique link connected only to their study ID, and email addresses will not be stored in Qualtrics, so that no protected health information is stored on the Qualtrics platform.

We will use standard IRB-approved and HIPAA compliant measures to maintain patient confidentiality, privacy and data security. Data privacy and security procedures will include: a) training staff on data sensitivity and protocols for safeguarding confidentiality; b) storing and processing sensitive hardcopy in a secured, centralized location; c) securing sensitive hardcopy in locked files when not in use; d) removing names, addresses, and other direct identifiers from

hardcopy and computer readable data after they are not necessary for patient tracking and then using encrypted codes for subsequent identification of subjects; e) destroying all identifiable linkages to data after data accuracy has been verified and final analyses have been completed; f) using restricted logon identification and password protection computer protocols for all computerized entry, retrieval, and analysis.

7.0 STATISTICAL ANALYSIS

Primary Aims:

1. To test the hypothesis that STEP-YA improves insomnia symptoms (primary outcome) and mood (secondary outcome) in young adult cancer survivors.

2. To determine if improvement in these outcomes are superior in the coaching condition compared to the non-coaching condition. This is a randomized 2-arm trial evaluating the STEP-YA intervention when delivered with and without supplementary remote coaching session. Immediately after completing baseline assessment subjects will be randomized (1:1 by the Sealed Envelope system) to receive the STEP-YA intervention either, 1) alone (**Non-Coaching condition**), or 2) with the addition of 2 remote coaching sessions delivered in the two weeks following the intervention session. (**Coaching condition**). Randomization, with block size of 4, will be stratified by age category (20-29 years vs. 30-39 years). Primary endpoint is change in Insomnia Severity Index score from baseline to 8-weeks post-intervention. Secondary endpoint is change in mood symptoms on the Profile of Mood States-Short Form from baseline to 8-weeks post-intervention. Primary and secondary endpoints are change at 8 weeks; data collected at 4-week post-assessment will be analyzed using similar methods for descriptive and exploratory purposes.

Data analysis for this study will follow methods used for our recently completed clinical trial of in-person insomnia interventions delivered to cancer survivors (1R03CA201459). Change scores will be treated as continuous variables and primary analyses will compare the arms using 2-way analysis of variance with one between-subjects factor (Coaching vs. Non-Coaching) and one within-subjects factor (time). Cohen's d will be used to quantify within-group effect sizes and Hedges' g adjustment will estimate between-group effect sizes. Aim 1 will be addressed using a

within-subjects analysis including all participants to determine if the STEP-YA intervention is associated with significant changes in outcome measures over time. Aim 2 will be addressed with an analysis that includes both the within – and between-subjects factors as well as an interaction term to determine if the effect of the intervention differs between Coaching and non-Coaching groups (i.e. significant interaction term).

Sample Size/Power: To meet our aims we require 64 participants with evaluable data but will enroll 74 as a hedge against attrition. Our prior single-session educational interventions have demonstrated large effects of $d \geq 1.00$; the study is conservatively powered to detect an effect size of .52 (Primary Aim). With sample size of 64 (32 per arm), the study will have 80% power to detect an effect of this size within each arm ($\alpha=0.05$). To compare the relative improvement in the primary endpoint between arms, $N=64$ subjects will have 80% power to detect a difference of $d=0.62$ between arms ($\alpha=0.05$, one-sided).

Secondary Aim: *Explore participant variables associated with clinically significant response to the STEP-YA intervention.* Logistic regression will be used to identify demographic and sleep factors (e.g., age, severity of insomnia symptoms) associated with a reduction of ISI scores ≥ 6 points at 8 weeks. Variables identified in univariate analysis ($p<.10$) will be entered into a multivariable model estimating STEP-YA response from baseline variables. Analyses will explore these relationships separately in the two study arms; Pooled analyses including participants across arms will be conducted if univariate analyses indicate relationship of predictors and outcome are consistent.

Missing Data: Participants will be randomized after completing a baseline so complete baseline data are assured. Primary analysis will be an intent-to-treat analysis of randomized subjects. Based on experience using similar data collection methods, we anticipate minimal missing data ($<10\%$). If needed, we will use multiple imputation to account for missing data. Potential factors in the imputation model include baseline sleep and mood variables. Sensitivity analysis will be used to evaluate the potential impact of imputation on results.

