- 3) Intervention Delivery. After completing baseline measures, the participant will immediately receive the STEP-YA intervention session via videoconference. (See section 5.3 for a description of the STEP-YA intervention). During the session, both the participant and the interventionist will be blinded to whether the participant has been randomized to receive the coaching sessions.
- 4) Randomization: After completing the session, randomization will be performed using Sealed Envelope, a commercially available online software application for randomising patients into clinical trials. Participants will be randomized (1:1) to either: **1)** STEP-YA alone (non-coaching condition) or **2)** STEP-YA with the addition of 2 remote coaching sessions (coaching condition). Participants will then be informed of whether they were randomized to receive the coaching sessions, and will schedule their first telephone call (first coaching session for those in the coaching condition or 4-week follow-up for those in the non-coaching condition). Additionally, participants will be asked to provide preferences for all future contact and correspondence (i.e., phone, email, send secure, text, mail) and

these preferences and addresses/phone numbers will be recorded in the participant's record.

- 5) Session evaluation: Participants will receive a link to a questionnaire on which they will report on ease of use and acceptability, satisfaction, and credibility of the session. To promote completion of the questionnaire, participants will be encouraged to complete it while still in the Zoom session, but can choose to complete it at a later time. Participants will receive a \$10 gift card upon completion of this evaluation.

Coaching Sessions: Participants randomized to the coaching condition will receive 2 individualized remote coaching sessions 1, and again 2 weeks following their STEP-YA session. (See section 5.4 below for a description of the coaching sessions and timing).

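### Randomisation is stratified by age category, but the Aim 2 between-arm model leaves age category out; if age predicts change in ISI, the test is slightly conservative and a little precision is forgone

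*Combined protocol and SAP*

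**What the plan says.** Section 7.0 (Statistical Analysis) sets the allocation: "Randomization, with block size of 4, will be stratified by age category (20-29 years vs. 30-39 years". Section 5.2 gives the ratio: "Participants will be randomized (1:1) to either" STEP-YA alone or STEP-YA with coaching.

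The analysis paragraph of Section 7.0 then specifies that "primary analyses will compare the arms using 2-way analysis of variance with one between-subjects factor (Coaching vs. Non-Coaching) and one within-subjects factor (time". Aim 2 uses both factors "as well as an interaction term to determine if the effect of the intervention differs between Coaching and non-Coaching groups". Aim 1 is a "within-subjects analysis including all participants to determine if the STEP-YA intervention is associated with significant changes in outcome measures over time". The outcome for both aims is fixed by "Primary endpoint is change in Insomnia Severity Index score from baseline to 8-weeks post-intervention", with mood (POMS-SF) as the secondary endpoint.

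The sample size paragraph says "we require 64 participants with evaluable data but will enroll 74 as a hedge against attrition". It claims 80% power for a between-arm difference of d = 0.62 at a one-sided alpha of 0.05.

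Age category is in neither the primary model nor any sensitivity analysis of it. In the analyses, age is named only as an example of a candidate predictor in the exploratory logistic regression of response. The factors suggested for the imputation model are measures of sleep and mood at baseline; age category is not mentioned.

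**The concern.** Permuted blocks within age category make the two arms nearly identical in age mix. Any age-related part of the outcome therefore largely cancels from the difference between arms, and the true sampling variance of that difference falls. A model with no age term still counts the age-related variation as residual error, so its reported standard error is larger than the true one. The interval for the coaching effect is then wider than the design warrants, and the test rejects less often than its nominal level under the null.

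At stake is the precision of Aim 2. Section 1.2 says that the comparison is meant to show whether coaching could add to STEP-YA before it is carried into a Phase III trial. With 32 evaluable participants per arm, that interval will be wide in any case. Age also has to be in the model before the data are seen, because adding it afterwards would be a post hoc choice.

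**Working it through.** **Inputs from Section 7.0:** 64 evaluable, 32 per arm; d = 0.62; alpha 0.05 one-sided; two age strata; blocks of 4. **Assumed:** R², the share of variance in ISI change explained by age category, which the documents do not give; strata of equal size; d expressed in units of the total within-arm SD (set to 1).

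**Step 1. Reproduce the plan's figure.** The standard error of the difference is √(2/32) = 0.25, so the noncentrality is 0.62/0.25 = 2.48. The normal approximation gives Φ(2.48 − 1.645) = Φ(0.835) = 79.8%. The noncentral t with 62 df gives 79.0%. Both agree with the stated 80% to rounding, and neither uses an age term.

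**Step 2. Add age category.** The residual SD becomes √(1 − R²). The noncentrality becomes 2.48/√(1 − R²), with 61 df. The unadjusted standard error exceeds the adjusted one by the factor 1/√(1 − R²).

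**Step 3. Type I error without age.** Under exact balance the estimate has variance proportional to 1 − R², while the reported variance stays near 1. The effective critical value is therefore about 1.670/√(1 − R²): 1.670, 1.687, 1.713, 1.760 and 1.867. Referred to a t distribution with 62 df, these give about 5.0, 4.8, 4.6, 4.2 and 3.3%.

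**Step 4. Simulation** (N = 64, strata exactly balanced by arm, one-sided test), set beside the Step 2 formula:

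| R² | SE ratio | Power without age | Power with age (simulated) | Power with age (formula) | Type I error without age |
|---|---|---|---|---|---|
| 0 | 1.000 | 79.1% | 79.1% | 79.0% | 5.0% |
| 2% | 1.010 | 79.1% | 79.6% | 79.7% | 5.0% |
| 5% | 1.026 | 79.7% | 80.8% | 80.8% | 4.5% |
| 10% | 1.054 | 79.8% | 82.5% | 82.6% | 4.3% |
| 20% | 1.118 | 81.4% | 86.5% | 86.4% | 3.3% |

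The simulated type I errors differ from Step 3 by 0.2 points at most, which is of the order of simulation error.

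**Step 5. What each R² means.** With equal strata, the two age groups differ in mean ISI change by 2√R² SD: 0, 0.28, 0.45, 0.63 and 0.89 SD.

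**Step 6. Which age term matters.** With two time points (baseline and 8 weeks), the arm-by-time test is the between-arm comparison of D = (8-week score − baseline score). A main effect of age is the same at both times and cancels from D, so it cannot change this test. Age-by-time does not cancel; it is the age term in a model for D. In one simulated data set of 64, the standard error of the interaction was 0.439 with no age term, 0.439 with an age main effect, and 0.417 once age-by-time was added.

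**The case against.** The strongest case against the point is that its effect may be nil. A reader might infer from the mismatch that the standard errors are certainly too large and that the trial loses power. The documents do not support that. They give no association between age category and ISI change, and at R² = 0 the two analyses coincide. The outcome is a change score and eligible ages run only from 20 to 39, so the low end of the range deserves most weight. An R² of 10% needs an age gap of 0.63 SD, about the size of the coaching effect that the trial is powered to detect, and 20% needs a larger one. This objection stands, and it is why the point is conditional.

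A reader might also infer that the trial falls short of its planned power. It does not: the stated 80% is a plain two-group calculation that takes no credit for age adjustment, and it reproduces without it. Two-sided power is lower (68.5% by the t calculation), but that is not the test on which the sample size paragraph bases its figure.

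Nor does leaving age out waste the stratification. The arms stay balanced on age, and the estimate's true variance is reduced whichever model is fitted; unadjusted power even rises slightly, from 79.1 to 81.4% across the table. Incomplete blocks and attrition also weaken the conservatism: with 74 enrolled and 64 evaluable, simulated type I error at R² = 20% was 3.6%, against 3.3% under exact balance.

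What survives is that the plan chose age category for stratification, names age as a possible predictor of response, and gives no reason for omitting it from the comparison of arms.

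**Conclusion.** The point holds in a limited, conditional form. The Aim 2 model does not reflect the stratified allocation. If age category predicts ISI change, the reported between-arm standard error is too large, by about 1% at R² = 2%, 2.6% at 5% and 5.4% at 10%. The power forgone is then about 0.5, 1.1 and 2.7 points. At R² = 20%, an extreme case here, it is about 5 points.

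The error is in the safe direction: the coaching estimate is not biased and false positives are not increased. Aim 1 is a pooled within-subject change that does not compare randomised arms, so stratified allocation does not affect its standard error. These sizes rest on the assumed R² values, equal strata and exact balance. The point is worth acting on because the correction costs almost nothing and must be pre-specified, not because the trial's conclusions are at risk.

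**What to change.** In Section 7.0, amend the Aim 2 models for ISI and POMS-SF in one of two ways, which are equivalent for the baseline-to-8-week comparison:

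- model the 8-week change score with arm and age category (20-29 vs 30-39) as terms; or
- keep the mixed ANOVA and add both age category and its interaction with time.

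State explicitly that a main effect of age alone in the mixed ANOVA is not sufficient, because it leaves the arm-by-time test unchanged. Include age category in any imputation model, so that imputation and analysis are consistent. If the investigators prefer to leave age out, give the reason in the SAP.

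The cost is a sentence or two of text and one degree of freedom (61 instead of 62). If age turns out to be unrelated to change, power is essentially unchanged. No change to sample size, randomisation or data collection is needed.

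### A single block size of 4, stated in the protocol, weakens the session blinding: up to about one third of allocations can be foreseen by someone who sees the whole sequence

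*Combined protocol and SAP*

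**What the plan says.** Section 7.0 (Statistical Analysis) sets 1:1 allocation through Sealed Envelope and adds: "Randomization, with block size of 4, will be stratified by age category". The strata are 20 to 29 and 30 to 39 years. No other block size is given, and nothing says that the size is withheld from anyone. On numbers, the same section says: "To meet our aims we require 64 participants with evaluable data but will enroll 74 as a hedge against attrition".

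Section 5.2 (Methods) describes blinding while STEP-YA is delivered: "both the participant and the interventionist will be blinded to whether the participant has been randomized to receive the coaching sessions". It then lists randomisation as the fourth component of the same session: "After completing the session, randomization will be performed using Sealed Envelope". The participant is told the arm and books either a first coaching session or the 4-week follow-up. A session evaluation comes next, and participants are encouraged to fill it in before leaving the Zoom meeting. The section does not name who operates the randomisation, and it does not say whether the interventionist is still present when the arm is disclosed.

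Section 7.0 gives a different moment for randomisation: "Immediately after completing baseline assessment subjects will be randomized". Sections 5.1 and 5.2 both put it after the session.

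**The concern.** The plan names a safeguard, an interventionist who does not know the arm, and then states the one parameter that helps someone work the arm out. In a 1:1 block of 4, the fourth allocation is always fixed by the first three, and the third is fixed whenever the first two match. Arms become known one by one as participants are told, and with two strata and 74 participants the running sequence is easy to track. Nothing in the plan prevents session staff from doing so.

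Coaching versus no coaching is the only randomised comparison. The session is a 90-minute one-to-one meeting with guided planning, delivered to both arms. If effort in that session, or the order in which participants are scheduled, shifted with the expected arm, the difference would be mixed with the coaching effect, and the planned analysis of variance could not separate the two.

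**Working it through.** The plan states no predictability figure, so there is none to reproduce.

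**Inputs.** From Section 7.0: block size 4, ratio 1:1, two age strata, 74 enrolled. Assumed: the share *q* of earlier allocations that an observer sees, because the documents do not give it.

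**1. One complete block, fully informed observer.** There are six equally likely sequences: AABB, ABAB, ABBA, BBAA, BABA, BAAB. An allocation is certain when one arm is already full.

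- Positions 1 and 2: never certain.
- Position 3: certain in AABB and BBAA, 2/6 = 1/3.
- Position 4: certain in all six, 1.
- Expected number: 0 + 0 + 1/3 + 1 = 4/3 per block. Share: (4/3)/4 = 33.3%.

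**2. Best guess (always name the arm with more places left).** Accuracy by position is 1/2, 2/3, 2/3 and 1. The mean is (0.5 + 0.667 + 0.667 + 1)/4 = 70.8%, against 50% under full concealment.

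**3. Seventy-four participants in two strata, allowing for incomplete last blocks.**

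- Split 37/37: each stratum has 9 full blocks and one extra allocation, 9 × 4/3 + 0 = 12. Total 24.0, or 24/74 = 32.4%.
- Split 11/63: (2 × 4/3 + 1/3) + (15 × 4/3 + 1/3) = 3.0 + 20.33 = 23.33, or 31.5%.
- These are the highest and lowest totals over possible splits.

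**4. Observer who sees only some earlier allocations.** Suppose each is seen independently with probability *q*, and the observer knows where the block starts. Certainty requires having seen both allocations to the arm that is full. Position 3 is then certain with probability q²/3 and position 4 with probability q². The share is (q²/3 + q²)/4 = q²/3.

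| q (assumed) | Certain share | Of 74 |
|---|---|---|
| 1 | 33.3% | 24.7 (23.3 to 24.0 after step 3) |
| 1/2 | 8.3% | 6.2 |
| 1/3 | 3.7% | 2.7 |
| 1/4 | 2.1% | 1.5 |
| 0 | 0 | 0 |

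Simulation agrees (8.4%, 3.7% and 2.1% for the three middle rows).

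**5. Randomly varying sizes.** This used 4,000 simulated sequences of 37 in a stratum. The observer knows the set of possible sizes and every earlier allocation.

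| Block sizes | Certain | Best guess correct |
|---|---|---|
| 4 only | 32.4% | 70.3% |
| 4, 6 | 5.6% | 68.6% |
| 2, 4, 6 | 4.0% | 69.5% |
| 4, 6, 8 | 2.2% | 67.3% |

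Varying the sizes removes most of the certainty and very little of the guessing advantage.

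**The case against.** The strongest reply is that one third assumes an observer whom the documents do not describe. That person must know the block size, the stratum, the position in the block and every earlier allocation in that stratum. Section 5.3 speaks of interventionists in the plural, Section 5.4 gives coaching to separate paraprofessional coaches, and no one is named as operating the randomisation. If interventionists see only their own participants' results, step 4 shows how quickly the certain share falls. This stands, and it is why one third is given only as an upper bound.

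A reader might infer that the blinding is defeated, or that a third of allocations will in fact be known. The documents support neither. Even a fully informed observer is uncertain about two thirds of allocations. In the order of Section 5.2, consent, baseline measures and the whole session come before randomisation. The session follows a structured outline with a fixed slide deck and supervision by psychologists. These features narrow the routes to bias but do not prevent prediction.

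Two further limits hold. Participants learn their arm after the session whatever the block size, so any reporting bias in the self-reported insomnia score is unchanged by the remedy. And although the arms are open once disclosed, the documents do not use the term open-label or say which staff read the protocol during enrolment.

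Against this, randomisation and disclosure are listed as parts of the session itself, and no barrier to staff accumulating results is described. The weakness is therefore plausible, though its extent is unknown.

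**Conclusion.** The point holds as a modest weakness in allocation concealment that is cheap to correct. To a staff member who knows the block size and sees every earlier allocation in a stratum, up to about one third of allocations (23 to 24 of 74) are certain before the session. If half are seen, the figure is about 8%, or about 6 participants. The actual share depends on who sees the results, which the plan does not state.

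The exposure is confined to the coaching comparison in Aim 2. Aim 1 pools all participants within subjects and does not depend on allocation. The block size does not enter the stated power calculation. The documents give no basis for putting a number on any bias in the insomnia score, and none is claimed here.

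The conflict over timing bears on the same safeguard. If randomisation follows the session, no allocation exists while the session is delivered, and only prediction is at issue. If it follows baseline directly, an allocation already exists during the session, and the blinding depends wholly on keeping it hidden.

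**What to change.** - In the Sealed Envelope setup, use randomly varying block sizes within the age strata, for example 4 and 6. Take the sizes out of Section 7.0 and hold them in a document kept by the statistician. The protocol need say only that permuted blocks of varying size are used.
- State in Section 5.2 who runs the randomisation, who sees each result, and whether the interventionist has left before the arm is disclosed.
- Reconcile the timing of randomisation in Section 7.0 with Sections 5.1 and 5.2.

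The cost is a change to the list setup and a few sentences. The downside is slightly more possible imbalance: the worst case within a stratum is half the block size, so it rises from 2 to 3, or from 4 to 6 over both strata. The gain should not be oversold. It removes most of the certainty and the knowledge of the block size, while best-guess accuracy stays at about 67% to 70%. Limiting who sees earlier allocations is what reduces the guessing advantage.
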